7.4. Laboratory Evaluations

The Clinical Laboratory Tests are the following:

Hematology	Chemistry	Urine Dipstick/ Urinalysis ^a	Other
Hematocrit	Albumin	Blood	Serum β -hCG ^b
Hemoglobin	Alkaline phosphatase	Glucose	Urine Drug screen
Platelet count	ALT	Protein	Fecal calprotectin ^{c,d}
WBC (total and differential)	AST	Specific gravity	Serum tissue transglutaminase
RBC	Bicarbonate	Microscopic exam	antibody (IgA) ^d
	Calcium	pH	Coagulation (INR/PT/APTT) ^g
	Chloride	Color	
	Creatinine ^e	Urine pregnancy test (B-hCG) ^b	
	FSH		
	Glucose		
	Lipase		
	Potassium		
	Sodium		
	Total bilirubin		
	Direct bilirubin ^f		
	Blood urea nitrogen		
	Total cholesterol		

APTT = activated partial thromboplastin time; ALT = alanine aminotransferase; AST = aspartate aminotransferase;

^bhCG = β -human chorionic gonadotropin; INR = international normalized ratio; PT = prothrombin time; RBC = red blood cell count; WBC = white blood cell count

^a A sample for urinalysis and urine culture/sensitivity testing will be sent to the laboratory only if the urine dipstick performed at the site tests positive for the presence of leukocytes, nitrites, or blood cells.

^b Urine β -hCG will be tested for women of childbearing potential only. If urine β -hCG is positive, a serum β -hCG must be performed.

^c Optional at Screening only.

^d Performed at Screening only per inclusion criterion #8.

^e Estimated glomerular filtration rate will be calculated and reported by the central lab.

^f If total bilirubin is elevated above the upper limit of normal.

^g Only upon request from Principal Investigator (if ALT, AST and bilirubin are increased).

All continuous laboratory parameters will be summarized descriptively by absolute value at each visit by treatment group, together with the corresponding changes from baseline. All parameters will be summarized in SI units. For continuous laboratory parameters with values that have a qualifier of “<”, “>”, “≥”, or “≤” than a limit of quantification will be set to the quantification value (e.g. <0.03 will be set to 0.03).

The number and percentage of subjects with laboratory measurements outside of the central laboratory normal range will also be summarized by treatment group and visit. Shift tables from baseline to maximum post-baseline value, to minimum post-baseline value, last post-baseline value, and at each post-baseline visit will be provided for hematology and chemistry parameters to display low, normal, high, and missing values by treatment group in a 3-by-3 contingency table. Denominators for percentages will be the number of subjects with non-missing data at the specific assessment and baseline.

Maximum post-baseline total bilirubin will be presented (<2 and ≥ 2 x ULN) and plotted against maximum post-baseline ALT (<3, ≥ 3 - <5, ≥ 5 -<10, and ≥ 10 x ULN), expressed as multiples of ULN. This will be repeated to show maximum post-baseline total bilirubin against maximum post-baseline AST.

Data for subjects, who may potentially meet Hy's law, with ALT or AST ≥ 3 x ULN, and bilirubin ≥ 2 x ULN will be presented, which will include all visits for this subset of subjects. A line plot of liver biochemistry test results (including ALP, ALT, AST, total bilirubin, and GGT) over time will also be presented for this subset of subjects.

Urinalysis was performed at the central laboratory and the urine cultures were analyzed by local laboratories. A sample for the urinalysis and urine culture were assessed only if the urine dipstick performed at the site tests positive for the presence of leukocytes, nitrites, or blood cells. Urinalysis data will be summarized for each visit for both categorical and numeric results.

Any data outside the central laboratory normal reference ranges will be explicitly noted on the listings that are produced.

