If **any** of the following liver test abnormalities develop, study drug should be withheld immediately with appropriate clinical follow-up (including repeat laboratory tests, until a subject's laboratory profile has returned to normal/baseline status), and the event reported as an SAE:

- ALT or AST $> 8 \times$ upper limit of normal (ULN)
- ALT or AST $> 5 \times$ ULN and persists for more than 2 weeks
- ALT or AST $> 3 \times$ ULN and total bilirubin $> 2 \times$ ULN or international normalized ratio (INR) > 1.5
- ALT or AST $> 3 \times$ ULN with appearance of fatigue, nausea, vomiting, right upper quadrant pain or tenderness, fever, rash and/or eosinophilia ($> 5\%$)

Rechallenge may be considered if an alternative cause for the abnormal liver tests (ALT, AST, total bilirubin) is discovered and the laboratory abnormalities resolve to normal or baseline values. The Investigator and Sponsor's designated Medical Monitor must discuss and agree with any decision to rechallenge.

Rechallenge should not occur when the etiology of the liver test abnormalities is considered possibly drug-induced.

8.4.7.2. Criteria for Permanent Discontinuation of Study Drug in Association with Liver Test Abnormalities

Study drug should be discontinued permanently if **all** of the following 4 criteria are met (ie, potential severe drug-induced liver injury/Hy's law case):

- Total bilirubin increases to $> 2 \times$ ULN or INR > 1.5 **and**
- AST or ALT increases to $\geq 3 \times$ ULN **and**
- Alkaline phosphatase value does not reach $2 \times$ ULN **and**
- No alternative cause explains the combination of the above laboratory abnormalities; important alternative causes include, but are not limited to, the following:
 - Hepatobiliary tract disease
 - Viral hepatitis (eg, hepatitis A/B/C/D/E, Epstein-Barr virus)
 - Exposure to hepatotoxic agents/drugs or hepatotoxins, including herbal and dietary supplements, plants, and mushrooms;
 - Alcoholic hepatitis
 - Non-alcoholic steatohepatitis

- Autoimmune hepatitis

If an alternative cause for hepatotoxicity is identified, then it should be determined (based on the severity of the hepatotoxicity or event) whether study drug should be withheld or permanently discontinued as appropriate for the safety of the subject, following consultation with the Sponsor's designated Medical Monitor.

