14.3.2.3	Treatment-related TEAEs by Preferred Term	SAF		EOS
14.3.2.4	Treatment-Emergent Adverse Events by Preferred Term and Maximum Intensity	SAF		EOS
14.3.2.5	Treatment-Emergent Adverse Events Occurring in $\geq 2\%$ Subjects of Vibegron Arm and Greater Than the Placebo by Preferred Term	SAF		EOS
14.3.2.6	Treatment-Emergent Adverse Events with Grade ≥ 3 by Preferred Term	SAF		TL, EOS
14.3.2.7	Treatment-related TEAEs with Grade ≥ 3 by Preferred Term	SAF		EOS
14.3.2.8	Serious TEAEs by Preferred Term	SAF		EOS
14.3.2.9	Treatment-related Serious TEAEs by Preferred Term	SAF		EOS
14.3.2.10	Fatal TEAEs by Preferred Term	SAF		EOS
14.3.2.11	TEAEs Leading to Treatment Discontinuation by Preferred Term	SAF		TL, EOS
14.3.2.12	TEAEs of Special Interest by Preferred Term	SAF		EOS
14.3.2.13	Treatment-related TEAEs of Special Interest by Preferred Term	SAF		TL, EOS
14.3.2.14	Non-Fatal Serious TEAEs by Preferred Term	SAF		EOS

Title		Analysis Set	Programming Note	Deliverable
14.3.2.15	Hypertension TEAEs by Preferred Term and Pre-existing Hypertension	SAF	Search for the following terms hypertension PTs: Accelerated hypertension, Diastolic hypertension, Essential hypertension, Hypertension, Hypertensive crisis, Hypertensive emergency, Hypertensive heart disease, Malignant hypertension, Malignant hypertensive heart disease, Secondary hypertension, Supine hypertension, Systolic hypertension	EOS
14.3.2.16	Hypertension TEAEs by Preferred Term and Baseline Hypertension Status	SAF	Search for the following terms hypertension PTs: Accelerated hypertension, Diastolic hypertension, Essential hypertension, Hypertension, Hypertensive crisis, Hypertensive emergency, Hypertensive heart disease, Malignant hypertension, Malignant hypertensive heart disease, Secondary hypertension, Supine hypertension, Systolic hypertension	EOS
14.3.2.17	GI/IBS-related TEAEs by Preferred Term	SAF		EOS
14.3.2.18	List of Deaths	SAF		EOS
14.3.2.19	Listing of Treatment Emergent Serious TEAEs	SAF		EOS
14.3.2.20	Listing TEAEs Leading to Withdrawal or Interruption of Study Treatment	SAF		EOS
14.3.2.21	Listing of TEAEs of Special Interest	SAF		EOS

Title		Analysis Set	Programming Note	Deliverable
Laboratory data				
14.3.3.1	Hematology Laboratory Parameters	SAF	Include observed and CFB; include conventional units as well for hematocrit	EOS
14.3.3.2	Abnormal Classification of Hematology Laboratory Parameters	SAF		EOS

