14.3.3.3	Shift Table of L/N/H Classification for Hematology Laboratory Parameters from Baseline	SAF	Include max/min post-dose, by visit, last-post dose	EOS
14.3.3.4	Clinical Chemistry Laboratory Parameters	SAF	Include observed and CFB	EOS
14.3.3.5	Abnormal Classification of Clinical Chemistry Laboratory Parameters	SAF		EOS
14.3.3.6	Shift Table of L/N/H Classification for Clinical Chemistry Laboratory Parameters from Baseline	SAF		EOS
14.3.3.7	Maximum Post-baseline ALT and AST vs. Maximum Post-baseline Bilirubin	SAF		EOS
14.3.3.8	Listing of Subjects Potentially Met Hy's Law	SAF		EOS
Other Safety				
14.3.4.1	Vital Sign Parameters	SAF	Include all observed and CFB	EOS
14.3.4.2	Vital Sign Parameter Change from Baseline Shifts at 3 Consecutive Visits	SAF	SBP, DBP and PR	EOS
14.3.4.3	Vital Sign Parameter Change from Baseline Shifts at Week 12	SAF		EOS
14.3.4.4	Vital Sign Parameter Maximum Post-Baseline Change from Baseline	SAF		EOS
14.3.5.1	Physical Examination Shift from Baseline	SAF		EOS

[1] TL= Topline Results (priority delivery after DBL); EOS= End of Study

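### The SAP's potential Hy's law display selects on bilirubin alone, while the protocol definition also accepts INR > 1.5, so a rare case that qualifies only through INR would be left out of one listing and one figure

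*SAP*

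**What the plan says.** Protocol 8.4.7.2 requires permanent discontinuation when four criteria are all met, and it labels the combination a "potential severe drug-induced liver injury" or Hy's law case. The criteria are:

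- total bilirubin above 2 x "ULN or INR > 1.5";
- AST or ALT at least 3 x ULN;
- alkaline phosphatase below 2 x ULN;
- no alternative cause.

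Protocol 8.4.7.1 uses the same alternative for temporary withholding: ALT or AST above 3 x ULN with total bilirubin above 2 x "ULN or international normalized ratio (INR) > 1.5".

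SAP 7.4 sets out to present subjects who may meet Hy's law. It takes those "with ALT or AST ≥ 3 x ULN, and bilirubin ≥ 2 x ULN will be presented", and INR is not mentioned. Table 14.3.3.8 lists this subset and Figure 14.3.3.3 plots it. The figure title requires raised ALT or AST together with raised total bilirubin. The plotted tests named in SAP 7.4 are ALP, ALT, AST, total bilirubin and GGT.

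Coagulation tests, INR included, are not routine. Footnote g to the laboratory table in SAP 7.4, which matches Protocol Table 10-1, says they are done "Only upon request from Principal Investigator (if ALT, AST and bilirubin are increased".

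The visible text of SAP Section 9, on changes from the protocol, does not mention the narrower selection.

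**The concern.** A screen for potential cases should be at least as wide as the definition it screens for. The SAP's screen is, on every term but one: it sets no alkaline phosphatase limit, does not exclude alternative causes, and takes bilirubin at or above 2 x ULN rather than strictly above. INR is the only route by which a woman could satisfy the protocol definition and still not be selected.

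What is at stake is how the study report reads. Table 14.3.3.8 is titled as the listing of potential Hy's law subjects, so an empty table invites the conclusion that there were none. If the only case qualified through INR, the table would be empty although the protocol's definition had been met. The reader would have to join an event record to an INR value in another listing to find out.

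**Working it through.** There is no planned figure to reproduce, so the check sets the two rules side by side.

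| Term | Protocol 8.4.7.2 | SAP 7.4 | Can the SAP miss a protocol case here? |
|---|---|---|---|
| Transaminases | ALT or AST >= 3 x ULN | ALT or AST >= 3 x ULN | No, identical |
| Bilirubin | > 2 x ULN | >= 2 x ULN | No, SAP slightly wider |
| INR | > 1.5, as an alternative to bilirubin | not used | Yes |
| Alkaline phosphatase | < 2 x ULN | not applied | No, SAP wider |
| Alternative cause | none | not applied | No, SAP wider |

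**Step 1. Who is missed.** Any woman who meets the protocol definition through bilirubin has bilirubin > 2 x ULN. She therefore also satisfies >= 2 x ULN, and the SAP selects her. The missed group is exactly: ALT or AST >= 3 x ULN, INR > 1.5, bilirubin never reaching 2 x ULN, alkaline phosphatase < 2 x ULN, and no alternative cause.

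**Step 2. Add the testing rule.** Footnote g makes INR available on request when ALT, AST and bilirubin are all increased. Under planned testing the missed group shrinks to women with both transaminases above ULN (at least one >= 3 x ULN), bilirubin above 1 x ULN but below 2 x ULN, and a requested INR > 1.5. The bilirubin band is not empty, so the case can occur under the plan as written.

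**Step 3. Illustration, hypothetical values.** ALT 4 x ULN, AST above ULN, maximum bilirubin 1.5 x ULN, INR 1.8, alkaline phosphatase 1 x ULN, no alternative cause.

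- Testing rule: ALT, AST and bilirubin all increased, so INR may be requested.
- Protocol 8.4.7.2: INR 1.8 > 1.5, ALT 4 >= 3, alkaline phosphatase 1 < 2, no alternative cause. Four of four criteria are met.
- SAP 7.4: ALT 4 >= 3 is met; bilirubin 1.5 >= 2 is not. She is not selected.

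**Step 4. Where she would still be seen.**

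- Protocol 8.4.7.1: ALT 4 > 3 with INR 1.8 > 1.5 requires withholding and SAE reporting. An ALT or AST elevation that leads to withholding or discontinuation is also an AESI. She should be in Listings 14.3.2.19 (serious TEAEs) and 14.3.2.21 (AESIs), and in 14.3.2.20, "Listing TEAEs Leading to Withdrawal or Interruption of Study Treatment".
- Table 14.3.3.7, "Maximum Post-baseline ALT and AST vs. Maximum Post-baseline Bilirubin", and the scatter plots: she falls in ALT >= 3 to < 5 with bilirubin < 2 x ULN, where nothing separates her from a woman with an isolated transaminase rise.
- Listing 16.2.3.9, other laboratory results: coagulation sits in the Other column of the laboratory table, so her INR should be here. For flagging, SAP 7.4 says: "Any data outside the central laboratory normal reference ranges will be explicitly noted on the listings that are produced". That helps if the sample was read against a central laboratory range.

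**Step 5. Frequency.** The documents give no rate for any of these findings, so none is estimated.

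**The case against.** The strongest reply is that the two rules do different jobs. Protocol 8.4.7.2 decides whether a woman stops drug and includes a clinical judgement on cause that no laboratory selection can make. SAP 7.4 is a descriptive display and does not claim to reproduce that section. This is fair, and it is why the point is about completeness of a display and not about an incorrect analysis. It does not remove the mismatch: the display is framed around Hy's law and is otherwise at least as wide as the protocol definition.

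A second reply is that bilirubin is measured at every scheduled laboratory visit, whereas INR depends on who orders it. Selection through INR would inherit that unevenness. This also stands as a limitation, but it is no reason to disregard an INR above 1.5 that was measured.

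A third reply is that the event is very unlikely. Entry excludes ALT or AST > 2 x ULN and bilirubin > 1.5 x ULN (> 2.0 x ULN with Gilbert syndrome). The protocol reports no liver-toxicity concern to date, and about 200 women are randomized. That limits the importance of the point.

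Two stronger readings should be resisted. A reader might infer that an INR-only case would go unreported or that subjects are less well protected. The documents do not support this: withholding and discontinuation both use INR, and the event should reach the SAE, AESI and interruption listings. A reader might also infer that any woman with ALT or AST >= 3 x ULN and a prolonged INR is in the gap. Under planned testing INR follows only when ALT, AST and bilirubin are all raised. A case with normal bilirubin would need an INR obtained outside that rule, for example from the unscheduled safety samples allowed in Protocol 8.3.4.

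**Conclusion.** The point holds as a minor inconsistency between SAP 7.4 and Protocol 8.4.7.2. One of the two routes through the first Hy's law criterion is not screened, so a protocol-defined case reached only through INR would be absent from Table 14.3.3.8 and Figure 14.3.3.3.

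Its effect is confined to those two outputs. It has no bearing on efficacy, safety reporting, withholding or discontinuation. The conclusion rests on SAP 7.4 being programmed as written, and on Table 14.3.3.8 and Figure 14.3.3.3 using that rule, as their titles and the figure's programming note indicate. The statement that her INR remains visible assumes that Listing 16.2.3.9 includes coagulation results, which the laboratory table suggests but the listing does not spell out. This is a desirable correction, not a condition for accepting the plan.

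**What to change.** In SAP 7.4, select subjects with ALT or AST >= 3 x ULN and (total bilirubin >= 2 x ULN, or INR > 1.5 where measured). Every woman who meets Protocol 8.4.7.2 is then selected, because meeting it through INR presupposes a measured INR. The woman in the illustration is picked up.

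Change the title of Figure 14.3.3.3 to refer to elevated total bilirubin or INR. Show INR, where measured, in both Table 14.3.3.8 and the line plot; otherwise an INR-only subject would be plotted with no qualifying value on view.

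The cost is one clause, one title, a revised selection step and one added parameter in two outputs. No new data are collected.

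There is a small downside. Protocol Table 6-1 names no anticoagulant class, and Section 6.5.2 leaves other medication to the Investigator's discretion, so an anticoagulated woman with raised ALT or AST could be listed because of her treatment. INR ascertainment will also be uneven because the test is on request. Noting the qualifying criterion and any anticoagulant use in Table 14.3.3.8 would make both easier to read, but this is optional.

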7.5. Vital Signs

Vital sign data including blood pressure, pulse rate and body temperature will be collected at all study visits except for the safety telephone follow-up visit. Body weight will be measured at Screening, baseline visit and Week 12 and Height will be measured at Screening only. Blood pressure and pulse will be measured in triplicate at each visit. The average of triplicates will be used for summary.

For all parameters, absolute values and change from baseline will be presented for scheduled visits using descriptive statistics for continuous variables. In addition, the maximum post-baseline, change from baseline to the maximum post-baseline, and change from baseline to the end of treatment will be summarized for each of the vital signs.

To further investigate changes in SBP/DBP/pulse rate from baseline, the following tables will be prepared:

- Counts and percent of subjects in each group with at least a 5/10/15 CFB at 3 consecutive post-baseline visits and at Week 12 will be produced for all subjects, by pre-existing hypertension category (Yes/No) and by baseline hypertension category (Yes/No). If the percentage of subjects in a subgroup is less than 25% of the total population, the subgroup in question will be not included in summary
- CFB in Maximum post-baseline (including 95% CI of Mean)

A by-subject listing, sorted by subject identifier, will be presented including all vital sign results (scheduled or unscheduled).

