4.2.2. Reporting Conventions

General rules

In general, all collected safety data and any derived efficacy parameters from daily evening pain diary and daily bowel movement diary and PRO data will be presented in subject data listings, for all enrolled subjects. Listings will be ordered by treatment subject number, and assessment week or event date. The treatment group presented in listings will be based on the planned assignment, unless otherwise noted.

Summary tables will be provided for all randomized subjects. All demographic and baseline data will be presented by treatment arm and overall, unless otherwise specified. Efficacy, PRO and safety data will be presented by treatment arm only. In general, continuous variables will be summarized to include the population sample size (N), number of subjects with available data (n), arithmetic mean, SD, median, minimum, Q1, Q3 and maximum values. Categorical variables will be summarized by the population size (N), number of subjects with available data (n), number of subjects in each category, and the percentage of subjects in each category. Unless otherwise noted, the denominator to determine the percentage of subjects in each category will be based on the number of subjects with available data (n) in the analysis set of interest. Selective ordinal data may be summarized using both descriptive statistics and counts and percentages of subjects in each category, as appropriate.

The data analyses will be conducted using the SAS® System (SAS Institute Inc., Cary, NC) version 9.4 or above. The [REDACTED]’ standard operating procedures will be followed for the validation of all SAS programs and outputs.

Formats

Numeric data will be reported at the precision collected on the eCRF. The reported precision from non eCRF sources may be adjusted to a clinically interpretable number or decimal places.

Unscheduled Visits

Unscheduled visits will be assigned to a study visit using the all-inclusive windows defined in [Section 4.2.4](#). However, for by visit summaries, only the planned assessment time points will be summarized. Assessments at unscheduled visits will be included for “any time On-treatment” timepoints and in data listings, as well as algorithms to determine the maximum.

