4.3.4. Baseline and Change from Baseline

In general, the last recorded value on or prior to the date of double-blind treatment start will serve as the baseline measurement for efficacy endpoints while the last recorded value prior to first dose of double-blind treatment will serve as the baseline measurement for safety endpoints. The mean of the multiple values will be used as baseline for the following situations:

- If multiple measurements are scheduled on the same baseline day (i.e., blood pressure)
- If multiple measurements are collected on the same baseline day without the time or “repeat” status to differentiate the records

Change from baseline will be calculated as the post-baseline value minus the baseline value. Percentage change from baseline will be calculated as the change from baseline divided by the baseline value, multiplied by 100. If either the baseline or post-baseline value is missing, then change from baseline and percentage change from baseline will be set to missing.

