- Hypertension TEAEs by Pre-existing Hypertension (Yes vs No) and Baseline Hypertension (Yes vs. No). Hypertension TEAEs will be selected using the same list of preferred terms as specified in [Section 5.2](#).
- All TEAEs by PT occurring in at least 2% of subjects in the vibegron arm and greater than the placebo arm will be created and sorted by descending frequency in the vibegron arm.
- Gastrointestinal/IBS-related TEAEs by PT will be prepared and sorted by descending frequency in the vibegron arm. The final list of GI/IBS-related PT will be finalized and documented prior to database lock.

Adverse events of special interest for this study include:

- Adverse events suggestive of cystitis or urinary tract infection (UTI)
- Potential major cardiac and cerebrovascular events, including all cause death, myocardial infarction, cerebrovascular accident, hospitalization for unstable angina or chest pain, hospitalization for heart failure and coronary revascularization/angioplasty/stent
- Hypertension
- AEs consistent with orthostatic hypotension as confirmed by orthostatic vital signs
- Elevated serum aspartate aminotransferase (AST) or alanine aminotransferase (ALT) lab value requiring that study drug be temporarily withheld or permanently discontinued

Overall AE listing will include the treatment arm, start and stop dates/times of the AE, first dose and last dose dates/times of double-blind treatment and days on study relative to the day of first dose and last dose of double-blind study treatment. In addition, the listing will indicate if the AE is treatment emergent (Yes vs No), an AE is of Special Interest (Yes vs No) and include the onset period (See [Section 4.2.4.1](#) for the definition of the periods).

A Treatment related AE is defined as an AE for which the investigator classifies the AE as being “Probably Related” or “Possibly Related” to study treatment on Adverse Event CRF. Missing relationship and severity (intensity) will be imputed per [Section 4.2.2](#).

The following additional listings will be provided:

- Listing of deaths
- Listing of Serious TEAEs
- Listing of treatment-emergent AESIs
- Listing of TEAEs leading to withdrawal or Interruption of study treatment

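### SAP 7.5 plans a post-baseline maximum but no minimum for blood pressure and pulse, and threshold counts that read as rises, so seated falls have no per-subject summary by arm

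*SAP*

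**What the plan says.** SAP 7.5 plans five kinds of vital-sign output:

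- By-visit summaries: "For all parameters, absolute values and change from baseline will be presented for scheduled visits using descriptive statistics for continuous variables". Under SAP 4.2.2 the statistics are "arithmetic mean, SD, median, minimum, Q1, Q3 and maximum values", together with N and n.
- Extreme and end-of-treatment summaries: "the maximum post-baseline, change from baseline to the maximum post-baseline, and change from baseline to the end of treatment". The output list carries the extreme as Table 14.3.4.4, for the maximum only.
- Threshold counts for systolic pressure, diastolic pressure and pulse: subjects with "at least a 5/10/15 CFB at 3 consecutive post-baseline visits and at Week 12" (Tables 14.3.4.2 and 14.3.4.3). They are also split by pre-existing and by baseline hypertension.
- The change to the post-baseline maximum with a 95% confidence interval of the mean.
- A by-subject listing of every result, scheduled or not.

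SAP 4.3.4 fixes the sign: "Change from baseline will be calculated as the post-baseline value minus the baseline value". SAP 4.2.2 limits by-visit summaries to planned time points. It sends unscheduled assessments to any-time on-treatment time points, to listings and to the algorithms that find the maximum.

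For hematology and chemistry, by contrast, SAP 7.4 plans "Shift tables from baseline to maximum post-baseline value, to minimum post-baseline value, last post-baseline value" and shifts at each visit. SAP 7.3 lists "AEs consistent with orthostatic hypotension as confirmed by orthostatic vital signs" among the events of special interest. Protocol 8.3.2 has blood pressure and pulse taken seated after 5 minutes of rest.

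**The concern.** Vital signs are a secondary safety endpoint in both documents (Protocol 3, SAP 1.1.2), and neither says that only rises matter. Yet the outputs that reduce each woman to one value or one yes/no across visits cover the upward direction only. The laboratory section plans both extremes, and no reason is given for treating vital signs differently.

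The unscheduled readings sharpen this. Protocol 4.1 allows Unscheduled Visits for safety concerns. A high reading at such a visit can enter the maximum table, while a low reading has no matching table to enter.

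At stake is how well the report can say how many women in each arm had a fall in seated pressure or pulse. As planned, that would have to be worked out by hand from the listing.

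**Working it through.** The documents give no figure for the vital-sign summaries, so there is none to reproduce. The check has two parts.

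**1. Where would a seated fall appear?** Take a woman whose systolic pressure is well below baseline at Week 4 and back at baseline by Week 8.

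| Planned output | Does it register the fall? |
|---|---|
| By-visit change at Week 4 | Yes, as one value in the arm's distribution (mean, Q1, minimum) |
| Maximum and change to maximum | Hardly: a low reading is rarely the maximum |
| Change to end of treatment | No: she has recovered |
| Counts at 3 consecutive visits | No: one visit only, and the counts read as rises |
| Counts at Week 12 | No: recovered, and the counts read as rises |
| Listing | Yes, as a row |

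The counts read as rises because change is post-baseline minus baseline. A fall is then a negative change and cannot be at least +5, +10 or +15. Section 7.5 does not say whether an absolute change was meant.

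An unscheduled low reading is worse placed. Under SAP 4.2.2 by-visit summaries use planned time points only. SAP 4.2.4.2 does pass unscheduled values through the windowing rule, so one might be chosen for a visit if it lies closest to the nominal day. Otherwise it reaches the listing. Section 4.2.2 mentions any-time on-treatment time points, but 7.5 defines no such vital-sign output apart from the maximum.

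**2. How much would the planned summaries move?** All inputs here are assumptions: one baseline and four post-baseline readings (Weeks 2, 4, 8 and 12), independent, normal, with within-woman visit SD of 6, 8 or 10 mmHg. In the second scenario 10% of women have a true 20 mmHg fall at one random post-baseline visit.

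With no drug effect, the expected maximum of four independent normal readings lies 1.03 SD above their mean. The mean change to maximum is therefore 1.03 × SD = 6.2, 8.2 and 10.3 mmHg, and the mean change to minimum is the mirror image. Simulated results, no fall → with falls:

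| Summary | SD 6 | SD 8 | SD 10 |
|---|---|---|---|
| Mean change to maximum (mmHg) | 6.2 → 6.1 | 8.2 → 8.1 | 10.3 → 10.1 |
| Rise ≥ 10 at 3 consecutive visits | 3.0% → 2.8% | 6.2% → 5.8% | 9.0% → 8.5% |
| Minimum change ≤ -20 | 3.1% → 7.8% | 11.5% → 15.5% | 21.2% → 24.4% |

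The first two rows are planned and barely move. The third is not planned and moves by 4.7, 4.0 and 3.2 points.

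**3. Must decrease counts use the same rule as the increase counts?** Under the no-effect model:

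| Criterion | SD 6 | SD 8 | SD 10 |
|---|---|---|---|
| Rise ≥ 10 at 3 consecutive visits | 2.9% | 6.1% | 9.0% |
| Fall ≥ 10 at any visit | 29.9% | 42.6% | 50.6% |

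(The first row comes from a separate run, so it differs slightly from the table above.) The ratios are 29.9/2.9 = 10.3, 42.6/6.1 = 7.0 and 50.6/9.0 = 5.6. Set beside the existing counts, an any-visit decrease count would make falls look roughly 6 to 10 times as common as rises with no drug effect. The criteria have to match.

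**The case against.** Three stronger readings are tempting, and the documents support none of them.

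A reader might infer that the vital-sign analysis looks only at the maximum. It does not. Section 7.5 also plans values and changes at every scheduled visit, change to end of treatment, and a full listing. The by-visit tables show the first quartile, median and minimum by arm, so a shift in the lower half of the distribution at a scheduled visit would be visible. What is missing is the per-subject summary across visits.

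A reader might infer that hypotension in general is an event of special interest left unanalysed. The event is orthostatic hypotension confirmed by orthostatic vital signs, and it has its own reporting (Tables 14.3.2.1, 14.3.2.12 and 14.3.2.13, and the listings). Scheduled readings are seated, so a seated minimum would complement that event and could not measure it.

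A reader might infer that a maximum-only table misleads because it shows a rise from visit-to-visit variation alone. That rise occurs in both arms, and the placebo arm calibrates it. The 6 to 10 mmHg above is no bias in the comparison between arms.

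It can also be said that attention to rises is reasonable. Hypertension is itself an event of special interest, and Protocol 4.3 reports no clinically relevant differences from placebo in heart rate or blood pressure at 50 and 100 mg in overactive bladder. The laboratory parallel is loose as well, since those are low/normal/high shifts against reference ranges. All of this lowers the priority of the point. None of it supplies the missing minimum or states the direction of the counts.

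**Conclusion.** The point holds as a minor gap in descriptive safety reporting. Section 7.5 and Tables 14.3.4.2 to 14.3.4.4 provide a maximum but no minimum, and threshold counts with no stated direction that read as rises under SAP 4.3.4. Section 4.2.2 names the maximum as the only extreme that unscheduled readings feed. Falls in seated pressure or pulse, above all transient or unscheduled ones, therefore have no per-subject summary by arm.

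That conclusion rests on the text alone. The size depends on assumptions: with independent visit SDs of 6 to 10 mmHg and a one-visit 20 mmHg fall in 10% of women, the planned per-subject summaries shift by at most 0.2 mmHg or 0.5 points, against 3 to 5 points for a minimum-based share. Other fall sizes, fall frequencies or correlations between readings would change these figures. The primary analysis is unaffected.

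**What to change.** In SAP 7.5 and the matching tables:

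1. Add the post-baseline minimum and the change from baseline to it for systolic pressure, diastolic pressure and pulse, by arm, beside the maximum in Table 14.3.4.4. Include unscheduled readings as for the maximum, and add the minimum to the wording of SAP 4.2.2.
2. State that the existing 5/10/15 counts are increases.
3. Add decrease counts under the same criteria, at 3 consecutive post-baseline visits and at Week 12, in Tables 14.3.4.2 and 14.3.4.3.
4. If an any-visit count is wanted, show it for increases and decreases together.

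Item 1 is the one that catches transient falls. The counts in item 3 describe sustained falls or falls present at Week 12. No new data are needed. The cost is extra rows in tables already planned and slightly longer safety output.
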